7.4.3 Laboratory indexes

Table 7.4.3.1 Numbers and percentages of cases with normal laboratory indexes before treatment and abnormal laboratory indexes after treatment (SS) – blood routine test

	Treatment group		Control group		
Item	Case number	Percentage	Case number	Percentage	P value
Red blood cell -abnormal but					
without clinical significance					
Red blood cell -abnormal and with					
clinical significance					
White blood cell - abnormal but					
without clinical significance					
White blood cell - abnormal and					
with clinical significance					
Hemoglobin - abnormal but without					
clinical significance					
Hemoglobin - abnormal and with					
clinical significance					
Platelet count - abnormal but					
without clinical significance					
Platelet count - abnormal and with					
clinical significance					

Table 7.4.3.2 Numbers and percentages of cases with normal laboratory indexes before treatment and abnormal laboratory indexes after treatment (SS)—routine urine test

Table 7.4.3.3 Numbers and percentages of cases with normal laboratory indexes before treatment and abnormal laboratory indexes after treatment (SS) – liver function

The same as above

Table 7.4.3.4 Numbers and percentages of cases with normal laboratory indexes before treatment and abnormal laboratory indexes after treatment (SS) – renal function

The same as above

Table 7.4.3.5 Numbers and percentages of cases with normal laboratory indexes before treatment and abnormal laboratory indexes after treatment (SS) – blood fat and blood glucose

The same as above

Table 7.4.3.6 Numbers and percentages of cases with normal laboratory indexes before treatment and abnormal laboratory indexes after treatment (SS) – four items of blood coagulation

The same as above

Table 7.4.3.7 Numbers and percentages of cases with normal laboratory indexes before treatment and abnormal laboratory indexes after treatment (SS) – ECG

	Treatment group		Control group		
Item	Case number	Percentage	Case number	Percentage	P value
Abnormal Q wave					
Abnormal T wave					
Arrhythmia – atrial fibrillation					
Arrhythmia –ventricular premature					
beat					
Arrhythmia - ventricular					
tachycardia					
Arrhythmia - atrioventricular block					
/ bundle branch block					
Arrhythmia – other					
Others					
Number of cases with normal ECG					
before treatment and abnormal ECC	Ī				
after treatment					

Table 7.4.3.8 Crosstab for determining clincial significance of laboratory indexes before and after treatment (SS) – blood routine test – red blood cell – treatment group

Treatment group	After trea	atment			
		Abnormal but without	Abnormal and with		
Before treatment	Normal	clinical significance	clinical significance	Unchecked Loss	Total
Normal					
Abnormal but without					
clinical significance					
Abnormal and with					
clinical significance					
Unchecked					
Loss					
Total					

Table 7.4.3.9 Crosstab for determining clincial significance of laboratory indexes before and after treatment (SS) – blood routine test – red blood cell – control group

Study No.: Document No.: Table 7.4.3.11 Crosstab for determining clincial significance of laboratory indexes before and after treatment (SS) – blood routine test – white blood cell – treatment group

Table 7.4.3.13 Crosstab for determining clincial significance of laboratory indexes before and after treatment (SS) – blood routine test – white blood cell – control group

Table 7.4.3.12 Crosstab for determining clincial significance of laboratory indexes before and after treatment (SS) – blood routine test - hemoglobin –treatment group

Table 7.4.3.13 Crosstab for determining clincial significance of laboratory indexes before and after treatment (SS) – blood routine test - hemoglobin –control group

The same as above

Table 7.4.3.14Crosstab for determining clincial significance of laboratory indexes before and after treatment (SS) – blood routine test – platelet count – treatment group

The same as above

Table 7.4.3.15 Crosstab for determining clincial significance of laboratory indexes before and after treatment (SS) – blood routine test – platelet count – control group

Table 7.4.3.16 Crosstab for determining clincial significance of laboratory indexes before and after treatment (SS) –routine urine test – red blood test – treatment group

The same as above

Table 7.4.3.17 Crosstab for determining clincial significance of laboratory indexes before and after treatment (SS) –routine urine test – red blood test – control group

Table 7.4.3.18 Crosstab for determining clincial significance of laboratory indexes before and after treatment (SS) –routine urine test – white blood cell – treatment group

The same as above

Table 7.4.3.19 Crosstab for determining clincial significance of laboratory indexes before and after treatment (SS) –routine urine test – white blood cell – control group

Table 7.4.3.20 Crosstab for determining clincial significance of laboratory indexes before and after treatment (SS) –routine urine test – urine protein – treatment group

The same as above

Table 7.4.3.21 Crosstab for determining clincial significance of laboratory indexes before and after treatment (SS) –routine urine test – urine protein – control group

Table 7.4.3.22 Crosstab for determining clincial significance of laboratory indexes before and after treatment (SS) – liver function – AST – treatment group

Table 7.4.3.23 Crosstab for determining clincial significance of laboratory indexes before and after treatment (SS) – liver function – AST – control group

Table 7.4.3.24 Crosstab for determining clincial significance of laboratory indexes before and after treatment (SS) – liver function – AST – treatment group

The same as above

Table 7.4.3.25 Crosstab for determining clincial significance of laboratory indexes before and after treatment (SS) – liver function – AST – control group

Table 7.4.3.26 Crosstab for determining clincial significance of laboratory indexes before and after treatment (SS) – liver function – ALP – treatment group

The same as above

Table 7.4.3.27 Crosstab for determining clincial significance of laboratory indexes before and after treatment (SS) – liver function – ALP – control group

Table 7.4.3.28 Crosstab for determining clincial significance of laboratory indexes before and after treatment (SS) – liver function – TBIL – treatment group

The same as above

Table 7.4.3.29 Crosstab for determining clincial significance of laboratory indexes before and after treatment (SS) – liver function – TBIL – control group

Table 7.4.3.30 Crosstab for determining clincial significance of laboratory indexes before and after treatment (SS) – liver function – GGT – treatment group

The same as above

Table 7.4.3.31 Crosstab for determining clincial significance of laboratory indexes before and after treatment (SS) – liver function – GGT – control group

Table 7.4.3.32 Crosstab for determining clincial significance of laboratory indexes before and after treatment (SS) – renal function – BUN/UREA – treatment group

The same as above

Table 7.4.3.33 Crosstab for determining clincial significance of laboratory indexes before and after treatment (SS) – renal function – BUN/UREA – control group

Table 7.4.3.34 Crosstab for determining clincial significance of laboratory indexes before and after treatment (SS) – renal function – Cr – treatment group

The same as above

Table 7.4.3.35 Crosstab for determining clincial significance of laboratory indexes before and after treatment (SS) – renal function – Cr – control group

Table 7.4.3.36 Crosstab for determining clincial significance of laboratory indexes before and after treatment (SS) – renal function – UA – treatment group

同上 The same as above

Table 7.4.3.37 Crosstab for determining clincial significance of laboratory indexes before and after treatment (SS) – renal function – UA – control group

Table 7.4.3.38 Crosstab for determining clincial significance of laboratory indexes before and after treatment (SS) – blood lipid and blood glucose – TC – treatment group

The same as above

Table 7.4.3.39 Crosstab for determining clincial significance of laboratory indexes before and after treatment (SS) – blood lipid and blood glucose – TC – control group

 $\begin{tabular}{ll} Table 7.4.3.40 & Crosstab & for determining clinical significance of laboratory indexes before and after treatment (SS) – blood lipid and blood glucose – LDL-C – treatment group \\ \end{tabular}$

The same as above

Table 7.4.3.41 Crosstab for determining clincial significance of laboratory indexes before and after treatment (SS) – blood lipid and blood glucose – LDL-C – control group

Table 7.4.3.42 Crosstab for determining clincial significance of laboratory indexes before and after treatment (SS) – blood lipid and blood glucose – HDL-C –treatment group

The same as above

Table 7.4.3.43 Crosstab for determining clinical significance of laboratory indexes before and after treatment (SS) – blood lipid and blood glucose – HDL-C – control group

Table 7.4.3.44 Crosstab for determining clincial significance of laboratory indexes before and after treatment (SS) – blood lipid and blood glucose – TG – treatment group

Table 7.4.3.45 Crosstab for determining clincial significance of laboratory indexes before and after treatment (SS) - blood lipid and blood glucose - TG - control group

Table 7.4.3.46 Crosstab for determining clincial significance of laboratory indexes before and after treatment (SS) - blood lipid and blood glucose - GLU - treatment group

Table 7.4.3.47 Crosstab for determining clincial significance of laboratory indexes before and after treatment (SS) - blood lipid and blood glucose - GLU - control group

Table 7.4.3.48 Crosstab for determining clincial significance of laboratory indexes before and after treatment (SS) – four items of blood coagulation – PT – treatment group

Table 7.4.3.49 Crosstab for determining clincial significance of laboratory indexes before and after treatment (SS) – four items of blood coagulation – PT – control group

Table 7.4.3.50 Crosstab for determining clincial significance of laboratory indexes before and after treatment (SS) – four items of blood coagulation – APPT – treatment group

Table 7.4.3.51 Crosstab for determining clincial significance of laboratory indexes before and after treatment (SS) - four items of blood coagulation - APPT - control group

Table 7.4.3.52 Crosstab for determining clincial significance of laboratory indexes before and after treatment (SS) – four items of blood coagulation – TT – treatment group

Table 7.4.3.53 Crosstab for determining clinical significance of laboratory indexes before and after treatment (SS) – four items of blood coagulation – TT – control group

The same as above

Table 7.4.3.54 Crosstab for determining clincial significance of laboratory indexes before and after treatment (SS) – four items of blood coagulation – FIB – treatment group

The same as above

Table 7.4.3.55 Crosstab for determining clincial significance of laboratory indexes before and after treatment (SS) – four items of blood coagulation – FIB – control group

The same as above

Table 7.4.3.56 Crosstab for determining clincial significance of laboratory indexes before and after treatment (SS) – ECG-treatment group

Treatment group	After treatmen	t		
Before treatment	Normal	Abnormal	Loss	Total
Normal				
Abnormal				
Loss				
Total				

Table 7.4.3.57 Crosstab for determining clincial significance of laboratory indexes before and after treatment (SS) – ECG-control group

7.5 Exploratory analysis

7.5.1 Predicted subgroup analysis on primary indexes –subgroup with or without thrombolytic therapy Table 7.5.1.1 Improvement of daily life ability at 90 days after treatment –subgroup with thrombolytic therapy

		FAS		PPS	
		Treatment		Treatment	
item	index	group	Control group	group	Control group
mRS score at 90 days after	≤1 point n(%)				
treatment					
	>1 point n(%)				
	N (Missing)				
	Statistics				
	P value				
	Rate difference				
	95%CI				

Note: 1. Take CMH- χ^2 test to control central effect

Table 7.5.1.2 Improvement of daily life ability at 90 days after treatment – subgroup without thrombolytic therapy

		FAS		PPS	_
		Treatment		Treatment	_
Item	Index	group	Control group	group	Control group
mRS score at 90 days after	≤1 point n(%)				
treatment					
	>1 point n(%)				
	N (Missing)				
	Statistics				
	P value				
	Rate difference				
	95%CI				

7.5.2 Predicted subgroup analysis on primary indexes –baseline NIHSS score subgroups

Table 7.5.2.1 Improvement of daily life ability at 90 days after treatment –baseline NIHSS score 4-7 points subgroup

		FAS		PPS	
		Treatment		Treatment	
Item	Index	group	Control group	group	Control group
mRS score at 90 days after	≤1 point n(%)				
treatment					
	>1 point n(%)				
	N (Missing)				
	Statistics				
	P value				

		FAS		PPS	
		Treatment		Treatment	_
Item	Index	group	Control group	group	Control group
	Rate differenc	e			
	95%CI				

Table 7.5.2.2 Improvement of daily life ability at 90 days after treatment-baseline NIHSS score 8-14 points subgroup

		FAS		PPS	
		试验组		试验组	
项目	指标	Treatment	对照组	Treatment	对照组
Item	Index	group	Control group	group	Control group
mRS score at 90 days after	≤1 point n(%)				
treatment					
	>1 point n(%)				
	N (Missing)				
	Statistics				
	P value				
	Rate difference				
	95%CI				

Note: 1. Take CMH- χ^2 test to control central effect

Table 7.5.2.3 Improvement of daily life ability at 90 days after treatment -baseline NIHSS score 15-22 points subgroup

		FAS		PPS	
		Treatment		Treatment	_
Item	Index	group	Control group	group	Control group
mRS score at 90 days after	≤1 point n(%)				
treatment					
	>1 point n(%)				
	N (Missing)				
	Statistics				
	P value				
	Rate difference				
	95%CI				

Note: 1. Take CMH- χ^2 test to control central effect

7.5.3 Predicted subgroup analysis on primary indexes – TOAST type subgroups

Table 7.5.3.1 Improvement of daily life ability at 90 days after treatment – atherothrombotic stroke subgroup

		FAS		PPS	
		Treatment		Treatment	
Item	Index	group	Control group	group	Control group

		FAS		PPS	
		Treatment		Treatment	_
Item	Index	group	Control group	group	Control group
mRS score at 90 days after	≤1 point n(%)				
treatment					
	>1 point n(%)				
	N (Missing)				
	Statistics				
	P value				
	Rate difference				
	95%CI				

Table 7.5.3.2 Improvement of daily life ability at 90 days after treatment - cardioembolism subgroup

		FAS		PPS	
		Treatment		Treatment	
Item	Index	group	Control group	group	Control group
mRS score at 90 days after	≤1 point n(%)				
treatment					
	>1 point n(%)				
	N (Missing)				
	Statistics				
	P value				
	Rate difference				
	95%CI				

Note: 1. Take CMH-χ² test to control central effect

Table 7.5.3.3 Improvement of daily life ability at 90 days after treatment – small artery occlusive stroke subgroup

		FAS		PPS	_
		Treatment		Treatment	
Item	Index	group	Control group	group	Control group
mRS score at 90 days after	≤1 point n(%)				
treatment					
	>1 point n(%)				
	N (Missing)				
	Statistics				
	P value				
	Rate difference				
	95%CI				

Table 7.5.3.4 Improvement of daily life ability at 90 days after treatment – subgroup with ischemic stroke caused by other reasons

enasta sy other reasons		
	FAS	PPS

		Treatment		Treatment	
Item	Index	group	Control group	group	Control group
mRS score at 90 days after	≤1 point n(%)				
treatment					
	>1 point n(%)				
	N (Missing)				
	Statistics				
	P value				
	Rate difference				
	95%CI				

Table 7.5.3.5 Improvement of daily life ability at 90 days after treatment – subgroup with ischemic stroke of unknown causes

		FAS		PPS	
		Treatment		Treatment	_
Item	Index	group	Control group	group	Control group
mRS score at 90 days after	≤1 point n(%)				
treatment					
	>1 point n(%)				
	N (Missing)				
	Statistics				
	P value				
	Rate difference				
	95%CI				

Note: 1. Take CMH- χ^2 test to control central effect

7.5.4 Predicted subgroup analysis on primary indexes –subgroups for course of disease

Table 7.5.4.1 Improvement of daily life ability at 90 days after treatment – subgroup for course of disease≤12h

		FAS		PPS	
		Treatment		Treatment	
Item	Index	group	Control group	group	Control group
mRS score at 90 days after	≤1 point n(%)				
treatment					
	>1 point n(%)				
	N (Missing)				
	Statistics				
	P value				
	Rate difference				
	95%CI				

Table 7.5.4.2 Improvement of daily life ability at 90 days after treatment – subgroup for course of disease of 12-48h

		FAS		PPS	_
		Treatment		Treatment	
Item	Index	group	Control group	group	Control group
mRS score at 90 days after	≤1 point n(%)				
treatment					
	>1 point n(%)				
	N (Missing)				
	Statistics				
	P value				
	Rate difference				
	95%CI				

Table 7.5.4.3 Improvement of daily life ability at 90 days after treatment – subgroup for course of disease of 48-72h

		FAS		PPS	
		Treatment		Treatment	
Item	Index	group	Control group	group	Control group
mRS score at 90 days after	≤1 point n(%)				
treatment					
	>1 point n(%)				
	N (Missing)				
	Statistics				
	P value				
	Rate difference				
	95%CI				

7.5.5 Predicted subgroup analysis on primary indexes –subgroups for course of disease – imaging subgroups

Table 7.5.5.1 Improvement of daily life ability at 90 days after treatment – subgroup with cerebral infarction diagnosed by imaging examination

		FAS		PPS	
		Treatment		Treatment	_
Item	Index	group	Control group	group	Control group
mRS score at 90 days after	≤1 point n(%)				
treatment					
	>1 point n(%)				
	N (Missing)				
	Statistics				
	P value				
	Rate difference				
	95%CI				

Note: 1. Take CMH- χ^2 test to control central effect

Table 7.5.5.2 Improvement of daily life ability at 90 days after treatment - subgroup without cerebral infarction diagnosed by imaging examination

		FAS		PPS	
		Treatment		Treatment	
Item	Index	group	Control group	group	Control group
mRS score at 90 days after	≤1 point n(%)				-
treatment					
	>1 point n(%)				
	N (Missing)				
	Statistics				
	P value				
	Rate difference				
	95%CI				

Table 7.5.5.3 Improvement of daily life ability at 90 days after treatment – subgroup with hemorrhagic impression diagnosed by imaging examination

		FAS		PPS	
		Treatment		Treatment	
Item	Index	group	Control group	group	Control group
mRS score at 90 days after	≤1 point n(%)				
treatment					
	>1 point n(%)				
	N (Missing)				
	Statistics				
	P value				

		FAS		PPS	
		Treatment		Treatment	
Item	Index	group	Control group	group	Control group
	Rate difference				
	95%CI				

Table 7.5.5.4 Improvement of daily life ability at 90 days after treatment - subgroup without hemorrhagic impression diagnosed by imaging examination

		FAS		PPS	
		Treatment		Treatment	
Item	Index	group	Control group	group	Control group
mRS score at 90 days after	≤1 point n(%)				
treatment					
	>1 point n(%)				
	N (Missing)				
	Statistics				
	P value				
	Rate difference				
	95%CI				

Note: 1. Take CMH- χ^2 test to control central effect

7.5.6 Predicted subgroup analysis on primary indexes –subgroups for course of disease – random time subgroups

Table 7.5.6.1 Improvement of daily life ability at 90 days after treatment - subgroup for random time earlier than median random time

		FAS		PPS	
		Treatment		Treatment	
Item	Index	group	Control group	group	Control group
mRS score at 90 days after	≤1 point n(%)				
treatment					
	>1 point n(%)				
	N (Missing)				
	Statistics				
	P value				
	Rate difference				
	95%CI				

Table 7.5.6.2 Improvement of daily life ability at 90 days after treatment - subgroup for random time later than median random time

		FAS		PPS	
		Treatment		Treatment	_
Item	Index	group	Control group	group	Control group

		FAS		PPS	
		Treatment		Treatment	
Item	Index	group	Control group	group	Control group
mRS score at 90 days after	≤1 point n(%)				
treatment					
	>1 point n(%)				
	N (Missing)				
	Statistics				
	P value				
	Rate difference				
	95%CI				

Note: 1. Take CMH- χ^2 test to control central effect

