rtPA Recombinant tissue plasminogen activator SAE Serious adverse event SFDA National Medical Products Administration TIA Transient ischemic attack TC Total cholesterol TCD Transcranial Doppler TG Triglyceride	RBC	Red blood cell		
SAE Serious adverse event SFDA National Medical Products Administration TIA Transient ischemic attack TC Total cholesterol TCD Transcranial Doppler TG Triglyceride	RCT	Randomized controlled trial		
SFDA National Medical Products Administration TIA Transient ischemic attack TC Total cholesterol TCD Transcranial Doppler TG Triglyceride	rtPA	Recombinant tissue plasminogen activator		
TIA Transient ischemic attack TC Total cholesterol TCD Transcranial Doppler TG Triglyceride	SAE	Serious adverse event		
TC Total cholesterol TCD Transcranial Doppler TG Triglyceride	SFDA	National Medical Products Administration		
TCD Transcranial Doppler TG Triglyceride	TIA	Transient ischemic attack		
TG Triglyceride	TC	Total cholesterol		
	TCD	Transcranial Doppler		
t-PA Tissue plasminogen activator	TG	Triglyceride		
	t-PA	Tissue plasminogen activator		
WBC White blood cell	WBC	White blood cell		

Protocol Synopsis

	1. The primary efficacy outcome was measured the			
	proportion of patients with modified Rankin Scale (mRS)			
	score ≤1 at 90 days after randomization. Subgroup analyses			
	for the primary outcome were conducted, based on TOAST			
	classification, reperfusion treatment, baseline NIHSS score			
	(4-7, 8-14 and 15-22), and AIS onset time to randomization			
	$(\leq 24, 24-48 \text{ and } 48-72 \text{ hours}).$			
	2. The secondary efficacy outcomes measured the proportion			
	of patients recovered to NIHSS 0-1 or reduction by 4 points			
	or more at 90 days, the proportion of patients with 85 or			
	more Bathel Index (BI) score at 90 days, distribution of			
Objective(s)	scores on the mRS (ordinal shift analysis) at 90 days,			
	incidence of ischemic cerebrovascular disease (ischemic			
	stroke, transient ischemic attack) and incidence of new			
	combination clinical vascular events (ischemic stroke,			
	hemorrhagic stroke, transient ischemic attack, myocardial			
	infarction, vascular death).			
	3. The following safety outcomes were also systematically			
	recorded: The incidence of adverse events, serious adverse			
	events, 12-lead electrocardiogram, physical examination and			
	laboratory test values (blood routine, urine routine, serum			
	biochemistry, coagulation).			
	A randomized, double-blind, placebo-controlled, and			

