6.2 Statistical method

6.2.1 General principle

SAS9.4 software is adopted for statistical analysis. All data are performed with two-sided test, and P value less than or equal to 0.05 (two-sided test) is considered with statistical difference. (Unless the special instruction)

Quantitative indexes are described with case number, mean, standard deviation, median, P25 (Q1), P75(Q3), minimum value (Min) and maximum value (Max).

Classification indexes are described with case number and percentage.

Comparison of general situation should be analyzed with appropriate method based on the type of indexes. Quantitative data should be analyzed with paired t test or Wilcoxon rank sum test; classification data with chi-square test or precise probability method, and ranked data with Wilcoxon rank-sum test or CMH test.

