6.2.6 Exploratory analysis

Take predicted subgroup analysis on primary indexes;

7. Results of statistical analysis

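### The protocol and SAP cut the onset-time subgroups differently, and the SAP's 19 subgroup tables rest on separate P values with no interaction test

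*Combined protocol and SAP*

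**What the plan says.** **Protocol synopsis, Objective(s).** Subgroup analyses of the primary outcome are listed by TOAST class, reperfusion treatment, baseline NIHSS and "AIS onset time to randomization". The time strata are ≤24, 24–48 and 48–72 hours. Protocol section 12 gives no subgroup method and no onset-time cut-points.

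**SAP 7.2.1.2 and 7.5.4.** The factor is called course of disease and the strata are ≤12, 12–48 and 48–72 hours. The first two subgroup tables are titled "subgroup for course of disease≤12h" and "subgroup for course of disease of 12-48h".

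**SAP 7.5.6.** A further pair of tables splits patients at a median, the first being the "subgroup for random time earlier than median random time". Random time is not defined.

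**SAP 6.2.6.** The whole subgroup method is one line: "Take predicted subgroup analysis on primary indexes". The section is headed as exploratory analysis.

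**SAP 7.5.1 to 7.5.6.** Each table has a test statistic, P value, rate difference and 95% CI, for FAS and for PPS. No interaction or homogeneity test and no multiplicity rule is given. The general rule in SAP 6.2.1 therefore applies to each: "P value less than or equal to 0.05 (two-sided test) is considered with statistical difference".

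**Protocol section 2 and SAP section 3.** Efficacy and safety by etiological subtype and by randomization time form part of the secondary objective.

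**The concern.** There are two separate problems.

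First, the two documents disagree on how patients are grouped by time from onset. Neither explains the difference or says which governs, and the SAP adds another time split whose variable is undefined and whose cut-point is unknown until the data are in. A reader of the results could not tell which time analysis was the planned one.

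Second, a question about whether the effect differs between subgroups is answered by comparing the effects, not by noting which subgroups reach 0.05. A significant result in one stratum and a non-significant one in another is what low power produces even when the true effect is the same throughout. Any statement that the treatment works in early but not late presenters, or in one stroke subtype but not another, would rest on these tables. They do not contain the test such a statement needs.

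**Working it through.** **1. Cut-points side by side.** Here *course of disease* is read as time from onset to randomization, which the SAP does not say.

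| Hours from onset | Synopsis stratum | SAP 7.5.4 stratum |
|---|---|---|
| up to 12 | first | first |
| 12–24 | first | second |
| 24–48 | second | second |
| 48–72 | third | third |

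Only patients at 12–24 hours change stratum, and the late stratum is the same in both documents. The documents give no distribution of onset times. If times were uniform over 0–72 hours (an assumption), 12/72 = 1/6 of 1,968 = 328 patients would move.

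**2. The plan's own figure.** Inputs from protocol 4.2: 40% v 47%, two-sided 0.05, power 80%, 20% dropout. The mean proportion is 0.435.

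n = [1.960·√(2·0.435·0.565) + 0.842·√(0.40·0.60 + 0.47·0.53)]² / 0.07² = 787 per arm after rounding up. Then 787/0.8 = 984 per arm, 1,968 in total. This reproduces the plan. The documents state no error rate for subgroups.

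**3. Number of subgroup tests.** Thrombolysis 2 + NIHSS 3 + TOAST 5 + course of disease 3 + imaging 4 + random time 2 = 19 tables, so 38 P values over FAS and PPS. Imaging is two factors (infarct seen, hemorrhagic impression), so there are seven factors.

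**4. Chance of at least one P ≤ 0.05 with no effect (FAS).** Treating k tests as independent gives 1 − 0.95^k:
- all 19 tables: 1 − 0.95^19 = 62%
- three onset-time strata: 1 − 0.95^3 = 14%
- onset-time strata plus the median split: 1 − 0.95^5 = 23%

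The factors divide the same patients, so the tests overlap. A simulation allows for this: 3,000 trials, N = 1,968, 40% in both arms, unstratified tests. Its subgroup shares are assumptions:
- thrombolysis 5/95%
- NIHSS 60/30/10%
- TOAST 50/8/30/2/10%
- infarct on imaging 90/10%
- hemorrhagic impression 3/97%
- onset uniform over 0–72 hours
- factors otherwise independent

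Results: any of the 19, 51%; onset-time strata, 14%; onset-time strata plus median split, 19%.

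**5. What separate P values show when the effect is uniform.** Take 47% v 40% in every stratum. Power with n per arm is Φ{[0.07√n − 1.960·√0.49155] / √0.4891}. Strata of 1/6, 1/3 and 1/2 of 984 per arm (164, 328, 492) have power 25%, 44% and 60%.

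- All three significant: 0.247 × 0.440 × 0.601 = 0.065
- None significant: 0.753 × 0.560 × 0.399 = 0.168
- Discordant: 1 − 0.065 − 0.168 = 77% (simulated 76%)

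Three equal strata, which the synopsis cut-points would give under uniform onset times, lead to 1 − 0.440³ − 0.560³ = 74%. Disagreement between strata is thus the usual result with no interaction present, under either set of cut-points.

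**6. After the change.** In the same simulation, one interaction test on a single set of three onset strata was falsely positive in 4.6% of trials with no effect and 5.0% with a uniform effect. One unadjusted test per factor gives 1 − 0.95^6 = 26% for six factors and 1 − 0.95^7 = 30% for seven (simulated 30%).

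**The case against.** The strongest reply is that the SAP files these analyses as exploratory and every table also gives a rate difference and 95% CI. The primary test, its type I error and the sample size do not depend on them. All of that stands and limits the severity. It does not reconcile the cut-points or supply a comparison between subgroups.

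It can also be said that course of disease and random time may not be the synopsis variable, and that the median split may be the table meant for the randomization-time objective. A median is also computed without reference to outcome. The documents leave this open, which is why definitions are needed before anything is deleted.

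Five stronger readings are tempting and not supported:

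- **That the SAP departed from cut-points fixed earlier.** The synopsis describes its subgroup analyses in the past tense, and nothing shows which set came first or that either was chosen after seeing results.
- **That chance findings on onset time are likely.** The 51–62% covers all 19 tables. Onset time alone carries about 14–19%.
- **That every subgroup test is stratified by centre.** In the text available, the CMH note follows only 8 of the 19 tables, and none of the three onset-time tables. SAP 6.2.4 may imply it for the rest, and notes may have been lost.
- **That small subgroups would lose a known share of patients to one-arm centres.** This needs centre and subgroup sizes that the documents do not give.
- **That the hemorrhagic-impression table can hold only protocol violators.** The notes to the flowcharts in protocol Appendix 1 and SAP 4.1.3 allow baseline MRI up to three days after randomization in radiology-subgroup centres. A correctly enrolled patient could therefore show hemorrhage on that scan.

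**Conclusion.** The concern holds as a point that should be corrected but does not threaten the primary result. The inconsistent cut-points, the undefined time variables and the absence of an interaction test are plain from the documents.

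The planned tables cannot establish that the effect varies by time, severity or etiology. For time and etiology, that falls short of a stated secondary objective. The 62% assumes independent tests. The 51%, the 19% and the 74–77% discordance depend on assumed subgroup shares, and the discordance also on the planned 47% v 40% effect. The need for an interaction test depends on none of these figures.

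**What to change.** Before unblinding:

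1. Reconcile the synopsis with SAP 7.2.1.2 and 7.5.4 on one set of onset-time cut-points, with a stated reason. The documents alone do not show which set should prevail.
2. Define *course of disease* and *random time*, giving the start and end of each interval. Justify the median split as a distinct analysis or remove it.
3. For each subgroup factor, report one treatment-by-factor interaction test. State its scale, and show risk differences so that the results match the primary hypothesis, which is a difference in proportions.
4. Present subgroup estimates with 95% CIs in a forest plot and drop the within-subgroup P values.
5. Label every interaction test exploratory in SAP 6.2.6, because six or seven unadjusted tests still carry a 26–30% chance of at least one false positive.

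The cost is changes to SAP wording and table shells (and synopsis wording if its cut-points change). No new data are needed and the sample size is unaffected.
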